Serious infections and reactivation of latent infections	
Available animal and human data suggest that blockade of IL-23 may be associated with an increased infection risk. Infections have been identified as adverse reactions of guselkumab, including respiratory infections, herpes simplex, tinea infections, and gastroenteritis.
	
Participants with a history of, or ongoing, chronic, or recurrent infectious disease, evidence of active or untreated latent opportunistic infections including tuberculosis (TB), will be excluded from the study (Section 5.2).
 
Participants receiving a live viral or bacterial vaccination within 12 weeks of first study intervention will be excluded from the study. In addition, participants must agree not to receive a live viral or live bacterial vaccination during the study and for 12 weeks after receiving the last dose of study intervention (Section 5.2).
 
Participants will be instructed to seek medical attention if they develop signs or symptoms suggestive of an infection, and investigators are instructed in the protocol to monitor for signs or symptoms of infections, including TB (Sections 8.2.10 and 8.2.10).
 
A participant's study intervention must be discontinued if an opportunistic infection including TB develops, and study intervention must be interrupted if the participant develops a serious infection, including but not limited to sepsis or pneumonia, and continuation or discontinuation of study intervention should be discussed and decided with the medical monitor or designee (Section 7.1).

Hypersensitivity reactions, including serious hypersensitivity reactions.	
Serious hypersensitivity reactions including anaphylaxis have been reported in postmarketing experience with guselkumab in PsO patients. Hypersensitivity, including anaphylaxis, urticaria
	
Participants with known allergy, hypersensitivity, or intolerance to guselkumab or its excipients will be excluded from the study.
 
Sites are instructed that before any administration of study intervention, appropriately trained

Potential Risks of Clinical Significance	Summary of Data/ Rationale for Risk	Mitigation Strategy

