The guselkumab dose to be evaluated in this protocol is 200 mg SC every 4 weeks from Week 0 to Week 48 for the main study (see Sections 4.2, Scientific Rationale for Study Design and Section 4.3, Justification for Dose). Based on a population pharmacokinetics (PK) analyses in patients with PsO or PsA, age (≥ 65 years) was not found to have significant impact on guselkumab apparent clearance following SC administration; therefore, guselkumab PK exposure in elderly participants is not expected to be substantially different from the non-elderly.

Potential risks of guselkumab, including those of serious infection and malignancy, and the risk of tapering participants of GCs are being addressed via judicious inclusion/exclusion criteria, frequent study visits to allow for close monitoring of patient safety, guidelines for participant management (including monitoring of clinical laboratory tests and treatment discontinuation criteria), detailed description of allowed and prohibited concomitant medications, and comprehensive medical monitoring of data by the sponsor during the conduct of the studies. In addition, a comprehensive safety monitoring plan with oversight from an independent Data Monitoring Committee (DMC) will be implemented to ensure the safety of guselkumab in participants with new-onset or relapsing GCA (Section 9.6).

In summary, the collective preclinical and clinical evidence for the anti-IL-23 mechanism of action in GCA, and the benefit-risk profile of guselkumab established to date in PsO and other immune mediated diseases, provide a strong scientific and clinical rationale for pursuing development of guselkumab in patients with GCA and for the investigation of guselkumab in this Phase 2 program. Taking into account the measures taken to minimize risk to participants in this study, the potential risks associated with guselkumab are justified by the potential benefits that may be provided to participants with GCA.

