8.3.7. Adverse Events of Special Interest

Any newly identified malignancy, case of active TB, or venous thromboembolism occurring after the first study intervention administration(s) in participants in this clinical study must be reported by the investigator to the sponsor or designee within 24 hours after being made aware of the event, according to the procedures in Section 10.4. Investigators are also advised that active TB is considered a reportable disease in most countries. These events are to be considered serious only if they meet the definition of an SAE.

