9.4.5. Safety Analyses

All safety analyses will be analyzed using the Safety Analysis Set population (refer to Section 9.3 for definition).

Adverse Events

The verbatim terms used in the CRF by investigators to identify AEs will be coded using the Medical Dictionary for Regulatory Activities. Any AE occurring at or after the initial

administration of study intervention through the end of the study is considered to be treatment emergent. All reported TEAEs will be included in the analysis. For each AE, the percentage of participants who experience at least 1 occurrence of the given event will be summarized by intervention group. In addition, comparisons between intervention groups will be provided if appropriate.

The following analyses of AEs will be used to assess the safety of participants in the main study:

- Number and proportion of participants with TEAEs by treatment intervention through Week 60
- Number and proportion of participants with TEAEs by system organ class and preferred term with a frequency threshold of 5% or more by treatment intervention through Week 60
- Number and proportion of participants with treatment-emergent SAEs by treatment intervention through Week 60
- Number and proportion of participants with reasonably related TEAEs as assessed by investigator by treatment intervention through Week 60
- Number and proportion of participants with infections, serious infections, and infections requiring oral or parenteral antimicrobial treatment through Week 60
- Number and proportion of participants with TEAEs leading to discontinuation of study intervention by treatment intervention through Week 60
- Number and proportion of participants with TEAEs temporally associated with an IV infusion by treatment intervention through Week 8
- Number and proportion of participants with injection-site reactions by treatment intervention.

Summaries, listings, datasets, or participant narratives may be provided through Week 28 and Week 60 by treatment intervention, for the above AEs, deaths, and severe AEs.

Similar safety analyses from Week 52 (LTE Week 0) through Week 112 (LTE Week 60) will be performed for participants in the LTE period.

Clinical Laboratory Tests

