5.7.2. Adverse Events

The verbatim terms used in the CRF by investigators to identify adverse events will be coded using the Medical Dictionary for Regulatory Activities (MedDRA). Any AE occurring at or after the initial administration of study intervention is considered to be treatment emergent. If the event occurs on the day of the initial administration of study intervention, and either event time or time of administration are missing, then the event will be assumed to be treatment emergent. If the event date is recorded as partial or completely missing, then the event will be considered to be treatment emergent unless it is known to be prior to the first administration of study intervention based on partial onset date or resolution date. All reported treatment-emergent adverse events will be included in the analysis. For each adverse event, the number and percentage of participants who experience at least 1 occurrence of the given event will be summarized by intervention group.

Safety data will be summarized and displayed by the following intervention groups:

- through Week 28

1. Placebo

2. Guselkumab

In addition, overall AEs will be also summarized and displayed by the following intervention groups:

- a. Placebo IV: participants receiving placebo during the study.
- b. Placebo SC: participants receiving placebo during the study.
- c. Guselkumab — Receiving 400 mg IV Induction Doses: participants receiving at least one administration of guselkumab 400 mg IV at Week 0, 4 and 8
- d. Guselkumab — Receiving 200 mg SC Induction Doses: participants receiving at least one administration of guselkumab 200 mg SC at Week 0, 4, and 8.

- through Week 60

1. Placebo

2. Guselkumab

- during the LTE period

1. Placebo

2. Guselkumab

The following summary tables will be provided for treatment-emergent adverse events:

- AEs
- AEs with a frequency threshold of 5% or more
- Serious AEs (SAEs)
- AEs leading to discontinuation of study intervention
- AEs by severity
- AEs by relationship to each study agent within a study intervention
- AEs temporally associated with an IV infusion
- Injection-site reactions

In addition to the summary tables, listings will be provided for participants who:

- Had SAEs
- Had AEs leading to discontinuation of study intervention
- Had AEs of severity
- Had temporally associated with infusion

- Had VTEs
- Had arterial thromboembolic AEs
- Had anaphylactic reactions and serum sickness reactions

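### SAP 5.7.2 leaves out the infection analysis required by protocol 9.4.5, and the antimicrobial-treated category cannot be obtained from any planned output.

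*SAP*

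**What the plan says.** Protocol 9.4.5 introduces its adverse event list with "The following analyses of AEs will be used to assess the safety of participants in the main study". One of the eight items is: "Number and proportion of participants with infections, serious infections, and infections requiring oral or parenteral antimicrobial treatment through Week 60". The section adds that similar analyses will be done for the LTE, and that summaries through Week 28 may be provided.

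SAP 5.7.2 states "The following summary tables will be provided for treatment-emergent adverse events" and names eight tables. A second list begins "In addition to the summary tables, listings will be provided for participants who" and covers, among others, serious adverse events, events leading to discontinuation of study intervention, venous and arterial thromboembolic events, suicidality, COVID-19 and death. Neither list has an infection item. Elsewhere in the SAP, the only infection-specific output is for COVID-19 (Appendix 7).

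On the relation between the two documents, protocol 9.4 says the SAP will describe the section's analyses in more technical detail. SAP Section 1 says that it covers the methods for all planned safety analyses.

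On the importance of infection, protocol 2.3.1 says "Infections have been identified as adverse reactions of guselkumab, including respiratory infections, herpes simplex, tinea infections, and gastroenteritis", and protocol 2.3.3 refers to "Potential risks of guselkumab, including those of serious infection and malignancy".

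**The concern.** The SAP should expand the protocol's safety analyses, and here it shortens the list. The lost item is the only one on that list about a specific known risk of the drug other than administration reactions. It concerns participants who start on 20 to 60 mg/day of prednisone or equivalent, and protocol 2.3.1 itself notes a possible increase in infection risk when guselkumab is combined with immunosuppressive treatment.

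If programming follows the SAP as written, one committed safety summary is not produced and two are left without a definition. A grouping written later, after sponsor staff have seen unblinded data at the Week 28 lock, would be a post hoc choice of what counts as an infection.

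**Working it through.** No figure in the plan is in dispute. The check sets the two lists side by side and then asks what the remaining outputs can supply.

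**1. List against list**

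| Protocol 9.4.5, main study | SAP 5.7.2 table |
|---|---|
| All TEAEs | Yes |
| TEAEs at 5% or more | Yes |
| Serious TEAEs | Yes |
| Related TEAEs | Yes (by relationship) |
| Infections, three categories | **None** |
| TEAEs leading to discontinuation | Yes |
| TEAEs associated with IV infusion | Yes |
| Injection-site reactions | Yes |
| (not listed) | By severity (added) |

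Seven of the eight protocol items are carried over and one table is added (7 + 1 = 8). The dedicated infection tables number 0 of 3.

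**2. What the other outputs can supply**

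- *Any infection.* SAP 5.7.2 says "For each adverse event, the number and percentage of participants who experience at least 1 occurrence of the given event will be summarized by intervention", so individual infection terms are shown by arm. The secondary safety endpoint in SAP 1.1 is by system organ class. If the coding dictionary places infections in one class, which the documents do not state, that class row approximates the count. The SAP does not name the row as the protocol's infection analysis and defines no grouping.
- *Serious infection.* The serious adverse event table and listing contain these events. The count can be approximated, again without a stated grouping.
- *Infection treated with oral or parenteral antimicrobials.* This is a participant-level count that joins an infection record to a treatment record with the right drug type and route. No table in 5.7.2 makes that join. SAP Appendix 4 plans concomitant medication summaries only for non-rescue GCA therapies. The count cannot be obtained from any planned output.

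**3. Are the data there?** Protocol 6.8 requires type of therapy, duration, dosing regimen, route and indication to be recorded for every concomitant therapy, and adverse events are collected throughout. The third category can be derived.

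**4. What the comparison could show.** Planned arms are 34 and 17 (SAP Section 3). The documents give no infection rate, so I assume the same rate p in both arms, from 20% to 40%. The 90% half-width for the risk difference is

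1.645 × √[p(1 − p)(1/17 + 1/34)], with 1/17 + 1/34 = 0.0882.

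- p = 0.20: 1.645 × √(0.16 × 0.0882) = 0.195
- p = 0.30: 1.645 × √(0.21 × 0.0882) = 0.224
- p = 0.40: 1.645 × √(0.24 × 0.0882) = 0.239

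An uncertainty of about 20 to 24 percentage points either way makes this a descriptive summary, not a test.

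**The case against.** The strongest reply is that little is really hidden. Every TEAE is tabulated by arm with no threshold, a system organ class summary is a stated endpoint, and serious events have both a table and a listing. SAP 5.7.2 does not say that its list is exhaustive, the protocol commitment still stands, and the DMC reviews unblinded safety data separately. Most of this stands for the first two categories, which is why I call them approximable and not lost. It does not reach the third. The SAP also marks open lists elsewhere (study periods in 5.7, laboratory tests in 5.7.3.1, subgroups in 5.8.8) and does not do so here, so a programmer would reasonably treat this one as complete.

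Three stronger readings are tempting, and the documents do not support them.

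- A reader might infer that infections would not be compared between arms at all, or that only a grouped table could show an imbalance. The all-TEAE, system organ class and serious event outputs contradict both.
- A reader might infer that the 5% threshold would hide rare infections, since 1 of 34 is 2.9%. The threshold governs one table; the general AE table has none.
- A reader might infer that malignancy and active TB, events of special interest in protocol 8.3.7, were dropped and have no output. Protocol 9.4.5 never listed an analysis of either. Protocol 7.1 requires study intervention to stop for active TB and, apart from a possible exception for up to two treated basal cell cancers, for malignancy. Most such events would therefore appear in the discontinuation table and listing, and serious ones in the serious event outputs. What is missing is a dedicated listing such as venous thromboembolism has.

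**Conclusion.** The point holds as a conflict between protocol and SAP over one committed analysis. None of the three infection categories has a dedicated table. Two can be approximated from other outputs, and one, infections treated with oral or parenteral antimicrobials, cannot be obtained from any planned output. The SAP should be corrected on this. The consequence is limited to safety reporting: the primary endpoint, its test and the sample size are unaffected, and the restored comparison would be descriptive.

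The conclusion about the omission and the antimicrobial category rests on the text alone. The approximation of the other two assumes the usual class-level layout of the adverse event tables, which SAP 5.7.2 does not spell out. The precision figures assume equal infection rates of 20% to 40%.

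**What to change.** In SAP 5.7.2, add by-arm tables through Week 60 of participants with (a) any infection, (b) a serious infection and (c) an infection treated with oral or parenteral antimicrobials. Use the same data cut as SAP 5.7, which counts LTE participants to Week 52 in the main-study summary. Add matching tables for the LTE, as protocol 9.4.5 foresees. Week 28 versions are optional.

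State how an infection is identified (the coded grouping or the investigator's classification) and how (c) is derived from adverse event and concomitant therapy records, including drug class, route, indication and timing. Fix these definitions before the Week 28 lock. If that lock has passed, fix them before the Week 60 lock and record the date.

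As an optional consistency point with protocol 8.3.7, place malignancy and active TB listings beside the venous thromboembolism listing.

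The cost is SAP wording, one derivation and three tables per period, from data already collected. No protocol amendment is needed.

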5.7.3. Additional Safety Assessments

5.7.3.1. Clinical Laboratory Tests

Clinical laboratory tests will be displayed for the participants included in the safety analysis set.

Descriptive statistics and graphical displays will be presented for selected chemistry and hematology laboratory tests at scheduled time points.

Change from baseline through Week 28 and through Week 60 for the main study, and from Week 52 (LTE Week 0) through Week 112 (LTE Week 60) will be summarized for chemistry and hematology tests and displayed by intervention group. A box plot of change from baseline through Week 28 and through Week 60 for the main study, and from Week 52 (LTE Week 0) through Week 112 (LTE Week 60) will be provided.

- **Hematology assessments** will include but are not limited to the following: hemoglobin, hematocrit, lymphocytes, neutrophils, platelet count, total and differential White Blood Cell (WBC) count.
- **Blood chemistry assessments** will include but are not limited to the following: chemistry panel (total and direct bilirubin, ALT, AST, alkaline phosphatase, albumin, total protein, calcium, phosphate, sodium, potassium, chloride, blood urea nitrogen/urea, and creatinine).

The National Cancer Institute's Common Terminology Criteria for Adverse Events will be used in the summary of laboratory data (Grade 0-4). The proportion of participants with post-baseline values by maximum toxicity grade for clinical laboratory tests will be summarized by study intervention group. Shift tables will be provided summarizing the shift in laboratory values from baseline to the end of the reporting period with respect to NCI-CTCAE grades. Participants with toxicity grades ≥ 2 will be listed.

For ALT and AST, highest postbaseline elevated liver function tests will be summarized by intervention group. In addition to the summary table, listings will be provided for participants with highest postbaseline elevated liver function tests ALT $\geq 3, \geq 5, \geq 8 \times \text{ULN}$, AST $\geq 3, \geq 5, \geq 8 \times \text{ULN}$, and participants meeting combined criteria (total bilirubin $\geq 2 \times \text{ULN}$, and either AST or ALT $\geq 3 \times \text{ULN}$), respectively.

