4. STUDY DESIGN

4.1. Overall Design

This is a randomized, double-blind, placebo-controlled, parallel, multicenter, interventional Phase 2 Proof-of-Concept study evaluating the efficacy, safety, PK, and immunogenicity of guselkumab for the treatment of active new-onset or relapsing GCA in adult participants.

A target of approximately 51 participants will be enrolled in this study. Participants will be randomly assigned into 2 treatment groups in a 2:1 ratio of guselkumab versus placebo.

- **Group 1: Guselkumab (200 mg SC every 4 weeks)**

Participants will receive guselkumab 200 mg SC every 4 weeks at Week 0 through Week 48.

- **Group 2: Placebo**

Participants will receive placebo SC every 4 weeks at Week 0 through Week 48.

Participant randomization will be stratified by new-onset and relapsing GCA (relapsing preferentially limited to 70% to ensure some enrollment of new-onset GCA but may be increased depending on the rate of enrollment of relapsing versus new-onset GCA), and by baseline GC dose (≤ 30 mg/day or > 30 mg/day).

The placebo comparator (in addition to standard-of-care background therapy of GCs) will be used in this study through Week 48 of the Main study to allow for blinded, placebo-controlled evaluation of the long-term efficacy and safety of guselkumab in participants with GCA. Participants on placebo that continue into the LTE will continue to receive placebo until the participant reaches Week 100 (LTE Week 48) or experiences a GCA flare, or until unblinding of the study due to completion of the main study, whichever occurs first.

The total duration of the study is up to 66 weeks for the main study: a screening period of ≤ 6 weeks, a 48-week main study treatment period, and a 12-week safety follow-up period after the last dose (a final efficacy visit 4 weeks after the last dose and a safety follow-up visit 12 weeks after the last dose). Participants that continue in the LTE period may continue in the study for a total duration of 112 weeks.

Participants that experience a flare should have a Flare visit with assessments performed according to the SoA preferably within 1 week of having the flare. In case a participant is diagnosed as having a flare during a study visit or shortly before a planned study visit, the Flare visit and regular visit can be combined. Overlapping procedures and assessments need only be performed once. The

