f) Have a chest radiograph (both posterior-anterior and lateral views, or per country regulations where applicable), taken within 3 months before the first administration of study intervention and read by a qualified radiologist (or pulmonologist in accordance with local regulations), with no evidence of current, active TB or old, inactive TB. A chest CT scan is also acceptable if obtained instead of a chest radiograph outside of the protocol.

15. Have screening laboratory test results within the following parameters, if one or more of the laboratory parameters is out of range, a single retest of laboratory values is permitted:

a. Hemoglobin	≥ 9 g/dL	SI: ≥ 90 mmol/L
b. White blood cells	$\geq 3.0 \times 10^3/\mu\text{L}$	SI: ≥ 3.0 GI/L
c. Neutrophils	$\geq 1.5 \times 10^3/\mu\text{L}$	SI: ≥ 1.5 GI/L
d. Platelets	$\geq 100 \times 10^3/\mu\text{L}$	SI: ≥ 100 GI/L
e. Serum creatinine	≤ 1.8 mg/dL	SI: ≤ 159 $\mu\text{mol/L}$
f. Aspartate aminotransferase (AST)	$\leq 3 \times \text{ULN}^*$	
g. Alanine aminotransferase (ALT)	$\leq 3 \times \text{ULN}^*$	

*For ALT/AST values >2 upper limit of normal (ULN) participants can only be included if bilirubin is normal.

General

16. Criterion modified per Amendment 3

16.1. Must sign an ICF indicating that the participant understands the purpose of, and procedures required for, the study and is willing to participate in the study.

17. Criterion modified per Amendment 3

17.1. Must sign a separate ICF if the participant agrees to provide an optional DNA sample for research (where local regulations permit). Refusal to give consent for the optional DNA research sample does not exclude a participant from participation in the study.

18. Must be willing and able to adhere to all specified requirements, including but not limited to completion of the required assessments, adherence to the visit schedule, and compliance with the lifestyle restrictions as specified in this protocol.

Inclusion criterion for LTE period

19. Participants are eligible for participation in the LTE period of the study if the participant:
 1. Has completed Week 52 visit of the main study, AND
has no signs and symptoms of active GCA, AND
completed treatment study intervention according to the protocol, AND
completed 26-week protocol defined GC-taper without the need to use rescue medication for GCA, AND
has not experienced a GCA flare through Week 52
 2. Has not had any study intervention-related SAE or severe AE

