1.2. Study Design

CNTO1959GCA2001 is a randomized, double-blind, placebo-controlled, parallel, multicenter, interventional Phase 2 Proof-of-Concept study evaluating the efficacy, safety, PK, and immunogenicity of guselkumab for the treatment of active new-onset or relapsing GCA in adult participants.

Main Study Treatment Period (Through up to Week 60)

A target of approximately 51 participants will be enrolled in this study. Participants will be randomly assigned into 2 study intervention groups with a 2:1 ratio for guselkumab versus placebo.

- **Group 1: Guselkumab (200 mg SC every 4 weeks)**

Participants will receive guselkumab 200 mg SC every 4 weeks at Week 0 through Week 48 in the Main study.

- **Group 2: Placebo**

Participants will receive placebo SC every 4 weeks at Week 0 through Week 48.

Participant randomization will be stratified by baseline disease status (new-onset and relapsing GCA; relapsing preferentially limited to 70% to ensure some enrollment of new-onset GCA but may be increased depending on the rate of enrollment of relapsing versus new-onset GCA), and by baseline GC dose (≤ 30 mg/day or > 30 mg/day).

The placebo comparator (in addition to standard-of-care background therapy of GCs) will be used in this study through Week 48 of the Main study to allow for blinded, placebo-controlled evaluation of the long-term efficacy and safety of guselkumab in participants with GCA. Participants on placebo that continue into the LTE will continue to receive placebo until the participant reaches Week 100 (LTE Week 48) or experiences a GCA flare, or until unblinding of the study due to completion of the main study, whichever occurs first.

The total duration of the study is up to 66 weeks of the main study: a screening period of ≤ 6 week, a 48-week main study treatment period, and a 12-week safety follow-up period after the last dose (a final efficacy visit 4 weeks after the last dose and a safety follow-up visit 12 weeks after the last dose). Participants that continue in the LTE period may continue in the study for a total duration of 112 weeks.).

[figure not shown]
Participants who develop a GCA flare should stop the protocol-defined GC taper and be given rescue therapy with GCs at the discretion of the investigator.

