5.7. Safety Analyses

All safety analyses for the main study will be based on the safety analysis set based on actual intervention received, unless otherwise specified. Safety analyses for the long-term extension will include participants who complete the Week 52 visits and are assessed to be in GC-free remission with at least one SC injection at Week 52 or later.

For all continuous safety variables, descriptive statistics by intervention group will include the N, mean, standard deviation, median, minimum, and maximum. Categorical variables will be summarized by intervention group using frequency counts and percentages.

Depending on the safety data, the cumulative safety data will be analyzed through different study periods which include but are not limited to through Week 28 and through Week 60 for the main study. The safety analyses through Week 60 for the main study will include safety data through Week 60 for participants not entering the LTE and safety data through Week 52 for participants continuing onto the LTE. Safety analyses from Week 52 (LTE Week 0) through Week 112 (LTE Week 60) will be performed for participants in the LTE period.

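### No planned by-arm laboratory table runs from baseline grade to worst postbaseline grade: the SAP 5.7.3.1 shift tables stop at the end-of-period value, and the maximum-grade and peak ALT/AST tables carry no baseline

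*SAP*

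**What the plan says.** SAP 5.7.3.1 plans shift tables in NCI-CTCAE grades "summarizing the shift in laboratory values from baseline to the end of the reporting period". The main-study reporting periods are Week 28 and Week 60, and a further period covers the LTE up to Week 112.

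The same section plans several other laboratory outputs:

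- a by-arm table of the maximum postbaseline toxicity grade (the sentence just before the shift tables);
- a listing of participants with grade 2 or higher (the sentence just after);
- change-from-baseline summaries and box plots for chemistry and hematology: "Change from baseline through Week 28 and through Week 60 for the main study", and for the LTE;
- a peak liver enzyme summary: "For ALT and AST, highest postbaseline elevated liver function tests will be summarized by intervention group", with listings at 3, 5 and 8xULN and for the combined bilirubin criterion.

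On timing, SAP 1.2 gives "Participants will receive guselkumab 200 mg SC every 4 weeks at Week 0 through Week 48" and then "a 12-week safety follow-up period after the last dose". Protocol 4.1 likewise places "a safety follow-up visit 12 weeks after the last dose". SAP 5.7 limits the Week 60 safety analysis to "safety data through Week 52 for participants continuing onto the LTE".

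On entry limits, Protocol 5.1 criterion 15 allows ALT and AST up to 3xULN. Above 2xULN, "participants can only be included if bilirubin is normal".

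**The concern.** A shift table is normally read as showing who got worse on treatment relative to where they started. If its second axis is the value at the end of the period, it shows who was still worse at that moment. The two differ most for abnormalities that are noticed and acted on. Protocol Appendix 9 calls for stopping study intervention at the listed liver thresholds and for following tests until they resolve, stabilize or return to baseline. A participant managed in that way is likely to be tabulated as unchanged.

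Protocol 2.3.1 names liver injury as a risk and transaminase increase as an identified adverse reaction, so ALT and AST are where the display matters most. The peak ALT/AST table does show the height of an elevation, but not whether it was new. Rising from the 2xULN entry band to 3xULN is a 1.5-fold change (3/2). Rising from 1xULN to 3xULN is a 3-fold change. The table would show the two alike.

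**Working it through.** **Step 1. Time from the last planned dose to the end of each period.** Study days are taken from the Protocol schedules of activities (1.3 and 1.4).

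| Period | Participants | Last planned dose before the end | End | Gap |
|---|---|---|---|---|
| Week 28 | all | Week 24, Day 168 | Day 196 | 28 days = 4 weeks |
| Week 60 | not entering LTE | Week 48, Day 336 | Day 420 | 84 days = 12 weeks |
| Week 60 | LTE entrants (data to Week 52) | Week 48, Day 336 | Day 364 | 28 days = 4 weeks |
| LTE | LTE participants | Week 100, Day 700 | Day 784 | 84 days = 12 weeks |

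The plan's own 12-week figure is reproduced. With the ±7-day window at both visits it ranges from (84 − 14)/7 = 10 to (84 + 14)/7 = 14 weeks. A gap of 4 weeks is one ordinary dosing interval, so the Week 28 table and the LTE entrants' Week 52 cut are on treatment.

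**Step 2. What each planned table shows for one assumed participant.** Baseline grade is 0, the on-treatment peak is grade 3, and the Week 60 grade is 0.

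| Output | Shows |
|---|---|
| Shift table as worded | 0 to 0 |
| Maximum-grade table | grade 3, no baseline |
| Listing of grade 2 or higher | participant listed |
| Baseline to worst postbaseline grade | 0 to 3 (not planned) |

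The elevation is reported, but no by-arm table reports it as a worsening from baseline.

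**Step 3. How often the end-of-period value would still show an episode, in this one table.** Assume that onset is uniform over the dosing window and that the episode lasts d weeks. The documents give neither onset nor duration, so d = 4, 8 and 12 are illustrative.

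- Week 28, onset in Weeks 0 to 28: d/28 = 4/28, 8/28, 12/28 = 14%, 29%, 43%.
- Week 60, non-LTE, onset by Week 48: max(0, 48 + d − 60)/48 = 0% for each d.
- Week 52 cut, LTE entrants, onset by Week 48: max(0, 48 + d − 52)/48 = 0/48, 4/48, 8/48 = 0%, 8%, 17%.

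The 0% at Week 60 follows from limiting episodes to 12 weeks. With d = 16 it is (48 + 16 − 60)/48 = 8%.

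**Step 4. Who falls in the 12-week row.** LTE entry (Protocol 5.1, criterion 19) requires study intervention completed per protocol and no intervention-related SAE or severe AE. A participant stopped for a liver signal is therefore in the non-LTE group. If that participant keeps the planned visits, the Week 60 sample comes more than 12 weeks after the last dose actually given. If the participant leaves the study, Protocol 7.2 places the early termination visit about 12 weeks after the last dose.

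**Step 5. Scale.** With the planned 34 and 17 participants, one person placed in the wrong category moves a rate by 1/34 = 2.9 points (guselkumab) or 1/17 = 5.9 points (placebo). This is the size of one case, not an estimate of how many there would be.

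**The case against.** The strongest reply is that nothing is lost. The maximum-grade table covers every graded test by arm, the listing names each participant at grade 2 or higher, and the peak ALT/AST outputs catch liver elevations. SAP 5.7.2 also tabulates and lists adverse events leading to discontinuation of study intervention. Protocol 9.4.5 requires the maximum-grade summary and the listing and does not ask for a shift table, so the SAP exceeds what the protocol demands. All of this stands.

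A reader might still infer four stronger things that the documents do not support.

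- **Resolved elevations go unreported.** They do not, for the reasons just given. Nor is the shift table the only display of change from baseline, since SAP 5.7.3.1 also plans summaries and box plots of change.
- **The Week 60 comparison is off drug for everyone.** SAP 5.7 ends LTE entrants' main-study data at Week 52, 4 weeks after the Week 48 dose.
- **The percentages in Step 3 measure what safety reporting misses.** They describe one table under assumed episode lengths.
- **The entry limit overlaps the first listing cut-off.** Entry is at or below 3xULN and the listing starts at or above 3xULN, so they meet only at exactly 3xULN. The 5x and 8x cut-offs are clear of it.

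Two further points reduce the weight. SAP Appendix 6 says that some tests have a separate grading range when baseline is abnormal, so the maximum grade may already allow for baseline in part. The grading table is not reproduced, so which tests are affected cannot be checked, and the rule does not reach an ALT/AST table in multiples of ULN. The shift wording could also be read as covering the whole period, in which case the sentence is ambiguous to a programmer and needs the same clarification.

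What remains is that the link between baseline and worst value would have to be rebuilt from listings, and a listing that starts at grade 2 omits shifts from grade 0 to grade 1.

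**Conclusion.** The point holds in a limited form. As worded, the shift tables show the end-of-period grade. The worst grade is tabulated without baseline, and baseline is tabulated without the worst grade. No planned by-arm output shows worsening from baseline to worst postbaseline grade.

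Severity is low. The tables are descriptive, no peak value is lost, and no estimate, test, power figure or decision rule changes. The SAP already takes the preferable approach for C-SSRS in 5.7.3.3, where the postbaseline summary rests on the most severe outcome and a shift table is built from it.

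The conclusion rests on the plain reading of the shift-table sentence and on laboratory samples being drawn at the period-end visits. The extracted schedule is too broken to confirm the Week 60 draw column by column, but the secondary safety endpoint covers laboratory tests through Week 60.

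**What to change.** In SAP 5.7.3.1:

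1. Define the shift tables as baseline NCI-CTCAE grade against worst (maximum) postbaseline grade within each reporting period (Week 28, Week 60, LTE), by arm. Keep the end-of-period shift as an optional extra, since it shows persistence or recovery.
2. Cross the highest postbaseline ALT and AST category with the baseline category, by arm. Baseline bands that fit criterion 15 are at or below 1x, above 1x to 2x, and above 2x to 3xULN.

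The cost is a short wording change and a modification to existing table programs. The data are already collected, and sample size, alpha and study conduct are unaffected.
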